Overall aim:	To better understand the epidemiology of, risk factors for and consequences of critical illness leading to improvements in risk models used to underpin national clinical audits for adult general critical care, cardiothoracic critical care and in-hospital cardiac arrest using data linkage with other routinely collected data sources	
Study setting	Adult critical care units, cardiothoracic critical care units and acute hospitals in England and Wales.	
Study participants	Patients admitted to an adult critical care unit or cardiothoracic critical care unit or experiencing an in-hospital cardiac arrest in an NHS acute hospital in England or Wales.	
Planned sample size	 Approximately 850,000 admissions (700,000 critical care unit survivors) for objective 1. Additional 170,000 admissions (150,000 critical care unit survivors) for external validation. Approximately 34,000 admissions to cardiothoracic critical care units (31,000 critical care unit survivors) for objective 2. Aditional 2,300 admissions (2,100 survivors) for external validation. Approximately 56,000 in-hospital cardiac arrests (10,000 survivors) for objective 3. Additional 16,000 in-hospital cardiac arrests (3,000 survivors) for external validation. 	
Planned study period	24 months	
Objectives	To improve risk models for adult general critical care by: (1a) developing risk models for mortality at fixed time-points and time-to event outcomes; developing risk models for	

- longer term chronic health outcomes of (1b) diabetes and (1c) end-stage renal disease; and (1d) developing risk models for subsequent health care utilisation and costs.
- 2. To improve risk models for cardiothoracic critical care by:
 (2a) enhancing risk factor data; (2b) developing risk models
 for longer term mortality; and (2c) developing risk models
 for subsequent health care utilisation and costs
- 3. To improve risk models for in-hospital cardiac arrest by: (3a) enhancing risk factor data; (3b) developing risk models for longer term mortality, health care utilisation and costs; (3c) developing risk models for subsequent critical care utilisation; and (3d) developing risk models for subsequent health care utilisation and costs
- 4. Immediate translation of the improved risk models into practice through: (4a) adoption into routine comparative outcome reporting for the national clinical audits; and (4b) communication of research output to providers, managers, commissioners, policy makers and academics in critical care

Study flow diagram

1. Background and rationale

High quality care is at the centre of the NHS.^[1] National clinical audit has a key role to play in ensuring high quality care, ^[2, 3]particularly in areas of health care, such as emergency and critical care, where patient choice does not, and cannot, play a significant part. Sophisticated and accurate risk prediction models are key in underpinning fair comparisons among health care providers. They can also enable risk-adjusted observational research and risk stratification in randomised controlled trials.

This study is a follow-on to a previous study that addressed risk prediction modelling in three clinical areas:

- adult general critical care;
- · adult cardiothoracic critical care; and
- in-hospital cardiac arrest.

The previous study made substantial steps forward in enabling fair comparisons among health care providers in all three areas, with immediate translation of the research outputs into routine practice, but has also identified important and essential new directions for further epidemiological and methodological research.

1.1. Adult general critical care

In 2005, ICNARC developed and validated the ICNARC model, [4] which underpins the risk-adjusted outcomes reported for the Case Mix Programme (CMP), the national clinical audit for adult general critical care co-ordinated by ICNARC. In the previous research study, the ICNARC model underwent external validation using data from critical care units in Scotland^[5] and was subsequently further developed to incorporate better handling of missing data (using multiple imputation), better modelling of physiology (using continuous non-linear modelling) and to make better use of available diagnostic information. This work has resulted in the next generation of the ICNARC model developed using data from over 150,000 admissions to 232 critical care units in a single year, which demonstrates excellent discrimination (c index 0.89) and improved risk stratification (net reclassification improvement 23%) in external validation data. This improved model is currently being incorporated into routine reporting for the CMP.

However, The focus of risk prediction modelling in adult general critical care, to date, has been on predicting mortality at discharge from acute hospital. While this is clearly an important and patient-centred outcome, the impact and consequences of critical care goes beyond hospital discharge to include longer-term mortality and morbidity. While routine data on longer-term, health-related quality of life for survivors of critical care are currently not collected/available, national clinical audits of chronic health conditions provide an ideal opportunity to better understand the impact and consequences of critical illness on these specific chronic health conditions gaining some insight into the wider impact of critical care on patients' subsequent health status.

Increased excess mortality following an episode of critical illness has been shown to continue for several years following hospital discharge. Death registrations are maintained by the Office for

National Statistics and made available to health researchers through the Data Linkage and Extract Service (DLES) at the Health and Social Care Information Centre (HSCIC). Data linkage between the CMP and death registrations will enable us to develop risk models to predict longer term mortality following an episode of critical illness.

The occurrence of hyperglycaemia is common among critically ill patients, regardless of diabetes status, and is associated with acute severity of illness and outcomes.^[6] Critical illness-related hyperglycaemia has previously been linked with subsequent development of Type 2 diabetes in small cohorts,^[7, 8] and data linkage between the CMP and the National Diabetes Audit will permit us to explore this in a much larger cohort and establish whether acute severity of hyperglycaemia or other risk factors are associated with the likelihood of developing Type 2 diabetes.

The occurrence of acute kidney injury (or acute renal failure) is common among critically ill patients and associated with high mortality,^[9] and has been strongly linked with subsequent end-stage renal disease.^[10] Data linkage between the CMP and the UK Renal Registry will enable us to evaluate this relationship in the UK and develop risk models to predict the requirement for long-term renal replacement among survivors of critical illness in the UK.

Survivors of critical care experience significant morbidity with substantial resultant healthcare resource use and costs. ^[11] Data linkage with Hospital Episode Statistics (HES) will enable us to estimate the cost of subsequent hospitalisations and its association with severity and/or duration of critical illness and other risk factors.

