1.2. Adult cardiothoracic critical care

Cardiothoracic critical care presents particular challenges for risk modelling, with a relatively low risk population, in comparison with other critical care sub-specialties. Patients may present with considerable physiological derangement due to the major insult of cardiac surgery, but not associated with the same increase in risk that would be anticipated in other critical care settings. For this reason, critical care unit admissions following cardiac surgery have been excluded from most previous critical care risk models. In the previous research study, we developed and validated a novel risk model for cardiothoracic critical care. The resulting model, based on 17,000 admissions to cardiothoracic critical care units, had excellent discrimination (c index 0.90) and this new, specific model for adult cardiothoracic critical care is being incorporated into routine reporting for cardiothoracic critical care units in the CMP alongside the main ICNARC model.

For cardiothoracic critical care, our work to date has focussed on the data items available in the CMP – a dataset designed to implement risk models for adult general critical care. Aside from patient demographics, these are almost exclusively post-operative risk factors. However, the majority of admissions to cardiothoracic critical care units are admitted following cardiac surgery and many pre- and intra-operative risk factors may also influence outcome for these patients. [13] The National Adult Cardiac Surgery Audit collects pre-operative risk factors and intra-operative process measures that would provide potentially important additional risk factor information to enhance our risk predictions among the cohort of patients admitted to cardiothoracic critical care units following cardiac surgery and to explore how risk changes along the patient journey.

Linkage to death registrations from ONS will also enable us to extend our risk models for cardiothoracic critical care to predict longer term mortality.

Data linkage with HES will enable us to estimate the cost of subsequent hospitalisations and its association with severity and/or duration of critical illness and other risk factors.

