Little is known on longer-term outcomes following in-hospital cardiac arrest and data linkage to ONS will enable us to extend our risk models to predict longer term mortality.

Finally, data linkage with HES will enable us to estimate the cost of subsequent hospitalisations and its association with the measured risk factors.

2. Study aim and objectives

The aim of the proposed study is to better understand the epidemiology of, risk factors for and consequences of critical illness leading to improvements in the risk models used to underpin national clinical audits for adult general critical care, cardiothoracic critical care and in-hospital cardiac arrest using data linkage with other routinely collected data sources.

Specific objectives are:

- To improve risk models for adult general critical care by: (1a) developing risk models for
 mortality at fixed time-points and time-to event outcomes (by data linkage between the
 CMP and death registrations from ONS); developing risk models for longer term chronic
 health outcomes of (1b) diabetes (by data linkage between the CMP and the National
 Diabetes Audit) and (1c) end-stage renal disease (by data linkage between the CMP and the
 UK Renal Registry); and (1d) developing risk models for subsequent health care utilisation
 and costs (by data linkage between the CMP and HES)
- To improve risk models for cardiothoracic critical care by: (2a) enhancing risk factor data (by data linkage with the National Adult Cardiac Surgery Database); (2b) developing risk models for longer term mortality (by data linkage between the CMP and death registrations from ONS); and (2c) developing risk models for subsequent health care utilisation and costs (by data linkage between the CMP and HES)
- 3. To improve risk models for in-hospital cardiac arrest by: (3a) enhancing risk factor data (by data linkage between NCAA and HES); (3b) developing risk models for longer term mortality, health care utilisation and costs (by data linkage between NCAA and ONS); (3c) developing risk models for subsequent critical care utilisation (by data linkage between NCAA and CMP); and (3d) developing risk models for subsequent health care utilisation and costs (by data linkage between NCAA, ONS and HES)

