- 4. Immediate translation of the improved risk models into practice through: (4a) adoption into routine comparative outcome reporting for the national clinical audits; and (4b) communication of research output to providers, managers, commissioners, policy makers and academics in critical care

3. Study design

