5.2.1.4. Hospital resource use and costs post-critical care (objective 1d)

Outcome defined as number of days in acute hospital (LOS), either during the original hospital episode (as identified from CMP data) or subsequent hospital episodes (as identified through data linkage with HES). We assigned a cost to every patient recorded in CMP by using the Reference Cost reported by all English hospitals .

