5.2.2.3. Hospital resource use and costs post-critical care (objective 2c)

Outcome defined as number of days in acute hospital, either during the original hospital episode (as identified from CMP data) or subsequent hospital episodes (as identified through data linkage with HES).

Patients included in the risk prediction model will be all those discharged alive from the cardiothoracic critical care unit.

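### The 1d and 2c outcome counts the original hospital episode, which contains the unit stay, so duration of critical illness would be partly correlated with itself if it is used as a predictor

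*Protocol*

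**What the plan says.** **The question.** Section 1.1 plans, through linkage with HES, to "estimate the cost of subsequent hospitalisations and its association with severity and/or duration of critical illness and other risk factors". Section 1.2 repeats the aim for cardiothoracic units: "cost of subsequent hospitalisations and its association with severity and/or duration of critical illness". In section 2, objective 1d is worded as "developing risk models for subsequent health care utilisation" and costs, and 2c is worded alike. The heading of section 5.2.1.4 reads "Hospital resource use and costs post-critical care (objective 1d", and that of 5.2.2.3 follows the same pattern for 2c.

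**The outcome.** Section 5.2.1.4 defines it as "number of days in acute hospital (LOS), either during the original hospital episode (as identified from CMP data) or subsequent hospital episodes", the latter identified through HES. It also says that each patient recorded in the CMP was given a cost based on national Reference Costs, with no restriction to use after the unit. Section 5.2.2.3 begins in the same way: "Outcome defined as number of days in acute hospital, either during the original hospital episode (as identified from CMP data". It restricts the population to patients who left the cardiothoracic unit alive. Neither section says whether critical care days are counted.

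**Predictors and use.** Neither section lists predictors. Appendix 1 includes unit admission and discharge dates, level-of-care days and organ support days in the CMP extract. Appendix 2 selects predictors by likelihood ratio tests and BIC. Objective 4a in section 2 plans "adoption into routine comparative outcome reporting for the national clinical audits" for the improved models in general.

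**The concern.** The stated question looks forward from critical care, but the defined outcome reaches back over it. Besides severity, duration is the only factor that sections 1.1 and 1.2 name for this analysis. On the face of the outcome definition, it is also a component of what is predicted.

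Two things are at stake. First, a positive coefficient for duration could be read as evidence that longer critical illness leads to heavier later hospital use, when some or all of it is the unit stay counted on both sides. Apparent fit would rise for the same reason. Second, if such a model were used to compare units, a unit that keeps similar patients longer would have its extra days explained by its own length of stay.

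**Working it through.** The protocol states no figure on this point, so there is nothing to reproduce. The check has four steps.

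**1. Which readings of the outcome overlap with duration?** Write U for critical care unit days and W for all other acute hospital days counted.

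| Reading of sections 5.2.1.4 and 5.2.2.3 | Contains U? |
|---|---|
| Original and later days summed | Yes |
| Original episode modelled alone, whole stay | Yes |
| Original episode counted only from unit discharge | No |
| Later episodes modelled alone | No |

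The text supports the first two at face value. The third needs a restriction that only the headings hint at. The fourth fits sections 1.1 and 1.2 but leaves out the original episode.

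**2. Size of the built-in part.** With Y = U + W,

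slope of Y on U = Cov(U + W, U) / Var(U) = 1 + slope of W on U.

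This also holds in least squares with other covariates in the model. If U and W are unrelated, the slope is exactly 1 and R-squared = Var(U) / (Var(U) + Var(W)). Illustrations, with all SDs and means assumed:

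- SD(U) = 6, SD(W) = 15: 36 / (36 + 225) = 0.138.
- SD(U) = 6, SD(W) = 25: 36 / (36 + 625) = 0.054.
- SD(W)/SD(U) = 1, 2, 3, 5: correlation of U with Y = 0.71, 0.45, 0.32, 0.20.
- Log-linear model, roughly 1/mean(Y) per unit day: 1/30 = 3.3% to 1/15 = 6.7% for mean totals of 30 to 15 days.

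**3. Would the selection rule remove it?** BIC keeps one extra term once its added R-squared exceeds about ln(n)/n. Section 3.2 gives 280,000 unit survivors for fitting the general model: 12.54 / 280,000 = 0.0045%. (Section 5.2.1.4 names no population, so using unit survivors for 1d is an assumption.) The synopsis gives 31,000 cardiothoracic survivors: 10.34 / 31,000 = 0.033%. Both thresholds are far below the illustrated 5% to 14%. If duration is offered as a candidate, selection will not screen out the overlap.

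**4. Simulation of the mechanism.** Assumed: 200,000 patients in 50 units, mean U 3.8 days (SD 3.6), mean W 9.9 days (SD 8.7), U and W linked only through severity, and one unit keeping its patients 2 days longer.

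| Outcome | Adjusted for | Coefficient of U | That unit, observed minus expected | O/E |
|---|---|---|---|---|
| U + W | severity | – | +1.67 days | 1.12 |
| U + W | severity and U | 0.99 | −0.28 days | 0.98 |
| W only | severity | – | −0.29 days | 0.97 |
| W only | severity and U | −0.01 | −0.28 days | 0.97 |

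The −0.28 is chance variation in W for that unit. Taking unit days out of the outcome removes the built-in coefficient. Leaving them in and adjusting for U hides the unit's extra stay.

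**The case against.** The strongest reply is that the protocol never specifies the faulty model. Sections 1.1 and 1.2 tie duration to later hospitalisations, which share no days with the unit stay, and they say severity and/or duration. Section 5.1.4 leaves the analysis plans to be finalised with the Clinical Advisory Groups, and a covariate list may properly sit in an SAP. The headings say post-critical care, and for 2c the population is formed at unit discharge, so a reader could take the original-episode days to start there. For predicting use after the unit, a completed unit stay is known and is a legitimate predictor.

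Most of this stands, and it limits the point in four ways.

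- A reader might infer that units' own length of stay will be adjusted away in audit reports. The documents do not support that: objective 4a is general, and no section makes duration an adjuster in a resource-use comparison.
- A reader might infer that a positive association is guaranteed. It is not: if longer unit stays replace ward days, the slope of W on U is negative and the total slope falls below 1, possibly to 0.
- A reader might infer that the question about subsequent use cannot be answered. It can, because later HES episodes are separately identifiable.
- The point does not carry over to objective 3d, whose rationale in section 1.3 names only the measured risk factors.

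The reply does not remove the conflict in the outcome definition. That definition is fixed in this document, includes the original episode without excluding unit days, and differs from the question posed in the rationale, objectives and headings.

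**Conclusion.** The point holds as an inconsistency with a conditional consequence. The outcome for 1d and 2c, as written, includes the unit stay, while the stated question concerns use after it. If duration of critical illness is used to predict total or original-episode days, the coefficient carries a built-in 1 day per unit day, added to whatever real relation exists between unit days and other days. The same applies to cost to the extent that the cost assigned covers the unit stay, which section 5.2.1.4 does not rule out.

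The algebra rests on no assumption about the data. The percentages, correlations and O/E values rest on assumed means and SDs and show only how the mechanism works. Any effect on comparison between units depends on a use of the model that the protocol allows but does not state. This should be settled before the models are built.

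**What to change.** In sections 5.2.1.4 and 5.2.2.3:

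- State whether critical care unit days and their cost count towards the outcome, and whether original and later episodes are summed or modelled separately.
- For any model containing duration of critical illness (unit days or organ support days), define the outcome as days and cost after critical care unit discharge, or in subsequent episodes only. Report unit days and unit cost separately.
- If a resource-use model whose outcome includes unit days is used to compare units under objective 4a, do not adjust it for duration or support days. Other predictors, including the pre- and intra-operative factors added under objective 2a, are unaffected.

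The cost is a change of wording. Unit and hospital dates are already in the CMP extract, so no new data are needed. The downside is a lower apparent model fit, because the part that came from counting the same days twice is gone.

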1.2. Adult cardiothoracic critical care

Cardiothoracic critical care presents particular challenges for risk modelling, with a relatively low risk population, in comparison with other critical care sub-specialties. Patients may present with considerable physiological derangement due to the major insult of cardiac surgery, but not associated with the same increase in risk that would be anticipated in other critical care settings. For this reason, critical care unit admissions following cardiac surgery have been excluded from most previous critical care risk models. In the previous research study, we developed and validated a novel risk model for cardiothoracic critical care. The resulting model, based on 17,000 admissions to cardiothoracic critical care units, had excellent discrimination (c index 0.90) and this new, specific model for adult cardiothoracic critical care is being incorporated into routine reporting for cardiothoracic critical care units in the CMP alongside the main ICNARC model.

For cardiothoracic critical care, our work to date has focussed on the data items available in the CMP – a dataset designed to implement risk models for adult general critical care. Aside from patient demographics, these are almost exclusively post-operative risk factors. However, the majority of admissions to cardiothoracic critical care units are admitted following cardiac surgery and many pre- and intra-operative risk factors may also influence outcome for these patients. [13] The National Adult Cardiac Surgery Audit collects pre-operative risk factors and intra-operative process measures that would provide potentially important additional risk factor information to enhance our risk predictions among the cohort of patients admitted to cardiothoracic critical care units following cardiac surgery and to explore how risk changes along the patient journey.

Linkage to death registrations from ONS will also enable us to extend our risk models for cardiothoracic critical care to predict longer term mortality.

Data linkage with HES will enable us to estimate the cost of subsequent hospitalisations and its association with severity and/or duration of critical illness and other risk factors.

